# 17.4.5. Secondary Outcome 4: Duration of oxygen supplementation

This outcome will assess if there is any evidence of a difference between groups in the duration of post-extubation oxygen supplementation of any kind, this includes all forms of non-invasive ventilation (NIV) and/ or high or low-flow oxygen.

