3.6.2 Secondary Outcomes/Endpoints

The secondary outcome measures for the trial (WP-A) are:

For efficacy:

- 1. duration of post-extubation non-invasive respiratory support (all forms of non-invasive ventilation: e.g. nasal CPAP and nasal high low oxygen)
- 2. duration of oxygen supplementation
- 3. number of trial interventions given (both poractant and placebo)
- 4. use of steroids to assist extubation
- 5. duration of stay on PICU and in hospital;
- 6. change over time from baseline of Ventilation Index (VI), Oxygenation Index (OI) and Oxygenation Saturation Index (OSI) while mechanically ventilated, & SpO₂/FiO₂ (SF) ratio.¹
- the score (value) of parent reported outcome measure of respiratory symptoms the "Liverpool Respiratory Symptom Questionnaire" (LRSQ) at 6m (+/-1m) and 12m (+/-1m) (20);

IRAS 220853 Page **20** of **87**

¹ VI and OI are validated physiological measurements reflecting respiratory function (gas exchange) normalised for level of respiratory support provided by MV, but require blood sampling(21). OSI is a validated physiological measurement reflecting respiratory function (gas exchange) normalised for level of respiratory support provided by MV that does not require blood sampling (41). The SF ratio is a non-invasive measure of respiratory function and can be calculated in situations where invasive blood gas monitoring and MV has ceased (22).

8. time from randomisation to meeting study criteria for readiness for Spontaneous Breathing Test

For safety:

- 1. failure to administer the intervention due to any adverse event during preparatory processes (tracheal toilet or BAL)
- 2. failure to complete administration of the intervention due to any adverse event during administration of the intervention (regardless of which arm of allocation)
- 3. incidents of 'air leak' (pneumothorax and pneumomediastinum) occurring before discharge from PICU
- 4. other adverse events and serious adverse events associated with the intervention
- 5. any need to replace the endotracheal tube
- 6. parent reported readmission to hospital (all causes) up to 90 days post randomisation
- 7. death during PICU admission
- 8. all-cause mortality at 90 days post randomisation

IRAS 220853 Page **21** of **87**

Table 1: Objectives and Outcome Measures

Objectives	Outcome Measures	Timepoint(s) of evaluation of this outcome measure (if applicable)

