## 9.2. Secondary outcomes

- Time from randomisation to meeting criteria for readiness for spontaneous breathing test (SBT)
- Number of trial interventions given
- Change from baseline of ventilation index, oxygenation index, and oxygenation saturation index whilst on MV
- Change from baseline of SpO2/FiO2 (SF) ratio
- Duration of oxygen supplementation
- Use of steroids to assist extubation
- Duration of post-extubation non-invasive respiratory support
- Duration of stay at Paediatric Intensive Care Unit (PICU) and in hospital
- Failure to administer intervention due to any adverse event (AE) during preparatory processes
- Failure to complete administration of intervention due to any AE during administration of intervention
- Incidence of pneumothorax or pneumomediastinum before discharge from PICU
- Any need to replace the endotracheal tube
- Parent-reported readmission to hospital
- Death during PICU admission
- All-cause mortality at 90 days post-randomisation
- Liverpool Respiratory Symptom Questionnaire (LRSQ) score

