#### 17.4.5.1. Derivation

The post-extubation oxygen supplementation details can be found on the Post Mechanical Ventilation follow up CRF. The start point for the duration of post-extubation oxygen supplementation will the date and time of final successful extubation as described in section 17.4.1.1, if this has been observed.

The end point will be the final date and time (MACRO variable PMV02DTD) that any type of oxygen supplementation (NIV, high-flow  $O_2^2$  or low-flow  $O_2^3$ ) is ended as indicated by the final observation for which the MACRO variable PMVS02SC (Supplementary O2 stopped?) = "Yes".

If oxygen supplementation is stopped and then restarted this time will be included in the overall time of post-extubation respiratory support. If no oxygen supplementation is recorded then time on postextubation respiratory support will be assumed to be zero.

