#### 17.4.5.2. Analysis

Descriptive statistics will be presented split by treatment and overall for the time from successful extubation to cessation of post-extubation oxygen supplementation. The summaries will be presented as median and interquartile range as the data is likely to be skewed.

The comparative analysis will be as described in 17.4.1.2 but will just involve the two-sample t-test, a linear mixed effects model will not be used for this outcome.

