#### 17.4.8.1. Derivation

The duration of stay at PICU will be calculated by taking the difference between the date/ time of randomisation taken from the Almac randomisation log and the date/ time of discharge from PICU (PDAISDTD) on the PICU Discharge CRF or the date of death (DNBDIDD) Day 90 Status CRF if the death occurred before PICU discharge. This can be expressed as:

 $T(PICU) = \begin{cases} PDAISDTD, & if dicharged \\ DNBDIDD, & if death occurs in PICU - T_{RAND} \end{cases}$ 

The overall duration of stay in hospital (including both time in PICU and time in hospital) will be calculated by taking the difference between the date/ time of randomisation taken from the Almac randomisation log on and the date/ time of hospital discharge (PDA90DTD) on the PICU or the date of

<sup>4 If date and time of death is required to calculate time in hospital or time in PICU then this will be estimated at 12:00 as death is only recorded as date.

death (DNBDIDD) Day 90 Status CRF if death occurred before hospital discharge. This can be expressed as:

 $T(Hospital) = \begin{cases} PDA90DTD, & if dicharged \\ DNBDIDD, & if death occurs \end{cases} - T_{RAND}$ 

Note that if death occurs during PICU then T(Hospital) = 0.

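### SAP 17.4.5 narrows oxygen duration, without explanation, to the time after extubation, so the arms lose a common time zero and earlier extubation on surfactant can show as longer oxygen need

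*SAP*

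**What the plan says.** Protocol 3.6.2 lists two separate efficacy outcomes. The first is limited to the period after ventilation: "duration of post-extubation non-invasive respiratory support (all forms of non-invasive ventilation". The second is simply "duration of oxygen supplementation". Table 1 of the protocol keeps the contrast and gives the timepoint for oxygen as N/A. SAP 9.2 also lists "Duration of oxygen supplementation" with no restriction, next to a respiratory-support outcome that does carry one.

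SAP 17.4.5 then makes the oxygen outcome the "duration of post-extubation oxygen supplementation of any kind". Section 17.4.5.1 says: "The start point for the duration of post-extubation oxygen supplementation will the date and time of final successful extubation". On the other end of the interval it says "The end point will be the final date and time (MACRO variable PMV02DTD) that any type of oxygen supplementation" stops, covering non-invasive ventilation, high-flow and low-flow oxygen. An infant with no oxygen recorded after extubation is given a duration of zero. Section 17.4.5.2 summarises the "time from successful extubation to cessation of post-extubation oxygen supplementation" and compares the arms with the two-sample t-test on log durations from 17.4.1.2.

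Other durations are handled differently. For intensive care stay, SAP 17.4.8.1 says: "The duration of stay at PICU will be calculated by taking the difference between the date/ time of randomisation" and discharge or death. Hospital stay also starts at randomisation.

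**The concern.** The oxygen clock starts at an event that happens after randomisation and that the treatment is designed to move. The primary outcome is the time from randomisation to that same event. If surfactant works on the primary outcome, its infants start the oxygen clock sooner after randomisation than controls do. Unless their oxygen also stops correspondingly sooner, the hours saved on the ventilator reappear as extra hours of oxygen.

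The SAP recognises this kind of problem elsewhere. In 17.4.4.2 it uses joint modelling for the ventilation and oxygenation indices because extubation may be informative. The oxygen outcome has no such protection, no version timed from randomisation and no sensitivity analysis. SAP section 11 sets out to test superiority on every outcome, so a trial that succeeds on ventilation time could also report significantly longer oxygen need as an artefact of the start point.

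Two smaller problems come from the same definition. Infants without an observed successful extubation have no start time and drop out, since SAP 17.1 allows no imputation. Durations set to zero cannot be log-transformed for the planned test.

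**Working it through.** **1. The 18 h shift in the plan's own figures.** The documents give no oxygen durations, so the only stated figure to reproduce is the sample size built on an 18 h reduction in ventilation (protocol 11.3).

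- Inputs: means 4.83 and 4.08 days, SD 2.5 days, two-sided alpha 0.05, 1:1 allocation.
- κ1 = 2.5/4.83 = 0.518 and κ2 = 2.5/4.08 = 0.613.
- ln(1+κ1²) = 0.2374 and ln(1+κ2²) = 0.3188, sum 0.5562.
- Log difference = ln(4.08/4.83) − ½(0.3188 − 0.2374) = −0.1688 − 0.0407 = −0.2095.
- n = (z_α/2 + z_β)² × 0.5562 / 0.2095², giving 99.5 → 100 per group at 80% power and 133.2 → 134 at 90%.
- 134/0.95 = 141.05 → 142 per group, 284 in total.

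All the stated figures reproduce, so 18 h is the right size of shift to examine.

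**2. The identity.** Let M be the time from randomisation to final extubation and E the time from randomisation to freedom from both ventilation and oxygen (E = M if no oxygen follows extubation). For every infant with an observed extubation, the SAP measure is P = E − M. For arm differences, surfactant minus control:

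ΔP = ΔE − ΔM.

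With ΔM = −18 h, and f the share of the saved hours by which the end of oxygen also comes forward, ΔE = −18f and ΔP = 18(1 − f).

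| f | ΔE, from randomisation | ΔP, SAP measure |
|---|---|---|
| 0 | 0 h | +18 h |
| 0.5 | −9 h | +9 h |
| 1 | −18 h | 0 h |

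For f strictly between 0 and 1 the two measures have opposite signs. At f = 0 a null shows as harm, and at f = 1 a real gain shows as nothing. The SAP measure favours surfactant only if the end of oxygen comes forward by more than 18 h.

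**3. Would the planned test pick this up?** This step rests on assumptions. In a simulation of 3,000 trials with 134 infants per arm, control ventilation time was log-normal with mean 115.9 h (4.83 × 24) and SD 60 h. Treated ventilation time was multiplied by 4.08/4.83. Control post-extubation oxygen was log-normal with an assumed mean of 24 to 120 h and coefficient of variation 0.8, independent of ventilation time. Every infant was extubated and had some oxygen afterwards. The test was the t-test on log durations.

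| Assumed control mean, post-extubation | f | SAP clock: ratio of geometric means | SAP clock: significantly longer on surfactant | Randomisation clock: ratio |
|---|---|---|---|---|
| 24 h | 0 | 2.02 | 100% | 1.00 |
| 48 h | 0 | 1.54 | 100% | 1.00 |
| 72 h | 0 | 1.37 | 98% | 1.00 |
| 120 h | 0 | 1.23 | 73% | 1.00 |
| 24 h | 0.5 | 1.54 | 100% | 0.94 |
| 48 h | 0.5 | 1.28 | 88% | 0.95 |
| 72 h | 0.5 | 1.20 | 61% | 0.95 |
| 120 h | 0.5 | 1.12 | 27% | 0.96 |

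At f = 1 the SAP clock gives a ratio of 1.00 at every assumed mean, while the randomisation clock gives 0.87 to 0.92.

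**4. Infants who drop out.** At the 1–2% mortality in protocol 10.2.3, 284 × 0.01 = 2.8 and 284 × 0.02 = 5.7, so about 3 to 6 infants if every death occurred on the ventilator. This is small beside the shift in time zero.

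**The case against.** The strongest reply is that the SAP's reading is legitimate. The protocol gives no start point for oxygen. Table 1 places this outcome under Secondary Objective 2, which concerns physiological indices and other modes of respiratory support. If other means other than mechanical ventilation, counting oxygen from the end of ventilation fits. The supplied protocol's amendment log ends at version 2.0, while the SAP states compliance with version 3.0 and its change control cites version 6.0, so later wording may differ. A reader might infer from the contrast with the non-invasive support outcome that the SAP breaches the protocol. The documents do not establish that. They do show that 17.4.5 adds a restriction absent from the SAP's own list in 9.2, without saying why.

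Second, calling the whole period from randomisation oxygen time would assume oxygen throughout ventilation, which the documents do not show. Oxygen on arrival in intensive care is recorded as a baseline variable that can differ between infants (SAP 17.2). This stands and governs how a replacement is labelled. It does not disturb the identity above, which uses only the time of freedom from both supports.

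Third, section 17.4.5 labels the measure as post-extubation, and ventilation time, intensive care stay and hospital stay are all timed from randomisation. A careful reader could set these side by side. That is a partial safeguard, but none of them measures when oxygen ends.

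Fourth, simply moving the start to randomisation while keeping the same oxygen-stop date would leave infants with no post-extubation oxygen without an end time, and would not rescue infants never extubated. This also stands, and explicit end rules are needed.

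**Conclusion.** The concern holds as an unexplained narrowing that gives the oxygen comparison a treatment-dependent time zero. If ventilation is 18 h shorter on surfactant and the end of oxygen comes forward by less than that, the SAP measure is longer on surfactant: by 18 h if the end does not move and by 9 h if it moves 9 h. If both move by 18 h it shows no difference. The direction follows from subtraction and needs no assumption about oxygen durations.

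Three stronger readings are not supported:

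- Surfactant need not appear to prolong oxygen. That depends on how far the end of oxygen moves, on which the documents are silent.
- The simulated rates are not forecasts. They rest on assumed means, spread and independence, and on an audit figure for total ventilation standing in for ventilation from randomisation.
- Randomisation is not abandoned. Infants are still analysed in their allocated group; what is lost is the common starting point.

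This is a secondary outcome, and the primary analysis is unaffected. The change is worth making because the direction of the reported effect can be wrong and the remedy is cheap.

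**What to change.** In SAP 17.4.5.1, make the comparative measure the time from randomisation (Almac log) to freedom from both ventilation and supplemental oxygen. It ends at the final `PMV02DTD` where `PMVS02SC` is Yes, or at final successful extubation (`OAODATXD`) if no post-extubation oxygen is recorded. The second rule keeps infants who need no further oxygen in the analysis and removes the zeros that cannot be logged.

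State a rule for infants who die or have no observed successful extubation, for example a censored sensitivity analysis along the lines of Additional analysis 1 in SAP section 19. The same rule should cover any infant with oxygen recorded after extubation but no stop time.

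Label the outcome as time to freedom from ventilation and oxygen, not as hours of oxygen. Keep post-extubation oxygen duration as a descriptive summary by arm, and add a sentence explaining how 17.4.5 relates to the wording in SAP 9.2 and the protocol version in force.

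The cost is SAP wording and a small programming change, since every time point is already collected. The downside is that the new measure contains ventilation time and so overlaps with the primary outcome; the report should say so and not treat it as independent confirmation.

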#### 17.4.5.1. Derivation

The post-extubation oxygen supplementation details can be found on the Post Mechanical Ventilation follow up CRF. The start point for the duration of post-extubation oxygen supplementation will the date and time of final successful extubation as described in section 17.4.1.1, if this has been observed.

The end point will be the final date and time (MACRO variable PMV02DTD) that any type of oxygen supplementation (NIV, high-flow  $O_2^2$  or low-flow  $O_2^3$ ) is ended as indicated by the final observation for which the MACRO variable PMVS02SC (Supplementary O2 stopped?) = "Yes".

If oxygen supplementation is stopped and then restarted this time will be included in the overall time of post-extubation respiratory support. If no oxygen supplementation is recorded then time on postextubation respiratory support will be assumed to be zero.

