6 STUDY POPULATION

6.1 Inclusion Criteria

- Term-born infants < 26 weeks old and preterm-born infants < 26 weeks corrected age[†]
- 2. Diagnosis of bronchiolitis (see below)
- 3. Requires conventional invasive MV via tracheal intubation
- 4. Parent or person with parental responsibility has given written informed consent for trial participation

Note: Infants with chronic lung disease of prematurity can be included in the trial.

† Correcting for prematurity is a well-established method for adjusting assessment of infants born prematurely who are anatomically, physiologically, immunologically and neuro-developmentally immature for their chronological age. In our study, term-born infants will be eligible for inclusion in the study up to chronological age of 26 weeks old (i.e. all those under 6 months old). Premature born infants have their age corrected to account for weeks of lost gestation, hence an infant born 12 weeks premature (i.e. before completing the 28th week of the 40 weeks of pregnancy) would still be eligible up to a chronological age of 38 weeks old (i.e. under 9 months), because that infant is still less than 26 weeks old when age is corrected for the premature birth.

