#### 8.8. Sequence and duration of all study periods

Clinical follow-up (daily data collection) will take place for the period of time between randomisation and discharge from hospital. All adverse events will be collected until 24 hours after the participant receives their final trial intervention. Non-serious adverse events occurring after 24 hours post-final intervention but before 90 days post-randomisation/discharge home/death will be reported if the local investigator believes that they may be related to the intervention.

Parent-reported outcomes will be collected via a brief questionnaire collecting hospital readmissions at 3 months post randomisation and the Liverpool Respiratory Symptom Questionnaire (LRSQ) at 6 and 12 months post-randomisation for participants recruited in seasons 1 and 2, and at 6 months only for participants recruited in season 3. The end of follow-up definition for each participant will therefore be 12 months post-randomisation for participants in season 1 and 2, or 6 months post-randomisation for participants in season 3.

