#### 17. Efficacy Evaluations

#### 17.1. Data Sets Analysed

The principle of intention-to-treat, as far as practically possible, will be the main strategy of the analysis adopted for the primary outcome and all secondary outcomes. These analyses will be conducted on all randomised participants, in the group to which they were randomised, and for whom the outcome(s) of interest have been observed/measured. No imputations will be made.

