#### 17.2. Demographic and Other Baseline Characteristics

Descriptive statistics will be presented split by treatment group and overall. Categorical data will be summarised by frequencies and percentages to one decimal place. Continuous data will be summarised to one decimal place by mean (standard deviation), median (interquartile range) and

#### Form prepared: 16/04/2024 v2.0 for BESS Page 14 of 30

range, irrespective of distribution. No formal statistical testing will be undertaken, but the clinical significance of any imbalance will be noted.

Baseline variables to be included:

- Whether infant premature or term-born
- Age/corrected age at randomisation
- Sex
- Weight
- Whether infant intubated upon arrival at PICU
- Whether infant on oxygen supplementation upon arrival at PICU
- Time on MV prior to randomisation
- Underlying viral/bacterial infection

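### The oxygen-duration rule in SAP 17.4.5.1 drops infants still on oxygen when data end, or scores them at an earlier stop, which would weaken a true treatment effect on this secondary outcome.

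*SAP*

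**What the plan says.** Protocol 3.6.2 names the outcome only as "duration of oxygen supplementation". The working definition is in SAP 17.4.5.1:

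- **Start:** "the date and time of final successful extubation as described in section 17.4.1.1, if this has been observed".
- **End:** the last time at which any oxygen support "is ended as indicated by the final observation for which the MACRO variable PMVS02SC (Supplementary O2 stopped?) = 'Yes".
- **Restart:** if oxygen is stopped and started again, that time counts towards the total.
- **Zero:** an infant with no oxygen recorded is given a duration of zero.

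Four other provisions decide what happens to an infant whose oxygen has not stopped:

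- SAP 8.8: "Clinical follow-up (daily data collection) will take place for the period of time between randomisation and discharge from hospital". Protocol 8.2 says the same.
- SAP 17.1 limits each analysis to participants "for whom the outcome(s) of interest have been observed/measured. No imputations will be made".
- SAP 17.4.5.2 compares the arms by the two-sample t-test on log-transformed duration alone.
- SAP 19 provides a Cox model with censoring, but only for the primary outcome.

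Protocol 6.1 adds: "Infants with chronic lung disease of prematurity can be included in the trial".

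**The concern.** The end rule presumes that every infant who received oxygen comes off it within the period of data collection. Nothing is written for an infant who does not. Leaving hospital on oxygen is foreseeable in a trial that admits infants with chronic lung disease of prematurity. The gap is wider than that group, however: it covers any infant discharged, transferred, withdrawn or dying while on oxygen.

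Whether an infant is lost or mis-scored depends on the outcome being measured. Those affected are mainly the infants who need oxygen longest. If surfactant shortens oxygen need, more controls than treated infants are affected, and the comparison understates the benefit. The SAP accounts for potentially informative drop-out of this kind for VI, OI and OSI (17.4.4.2), and it writes a rule for death in the length-of-stay outcomes (17.4.8.1). It does neither here.

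**Working it through.** **Step 1: apply the rules as written to an infant on oxygen at the last record.**

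| History | Record that 17.4.5.1 selects | Result |
|---|---|---|
| Oxygen never stopped | None | Outcome not observed; excluded under 17.1 |
| Stopped, restarted, never stopped again | The earlier stop | Duration too short; conflicts with the restart sentence in the same section |
| Stopped, restarted, stopped again | The last stop | Correct |
| No oxygen recorded | Zero rule | Not relevant to this gap |

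Neither of the first two rows keeps the true, longer duration.

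**Step 2: size of the effect of exclusion.** The documents give no distribution of oxygen time and no rate of discharge on oxygen, so there is no figure of the plan's own to reproduce for this outcome. From Protocol 11.3 I take only the arm size: 134/0.95 = 141.05, rounded up to 142 per arm, 284 in total. The rest is assumed:

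- log duration is normal with SD 1.0
- the true ratio of geometric means is 0.80, so the log effect is ln 0.80 = −0.2231
- infants beyond a common cut-off c leave on oxygen and are excluded
- all 142 per arm have a positive duration

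With control log durations N(0, 1) and treated N(−0.2231, 1), let q be the share of controls beyond c. Then c = Φ⁻¹(1 − q), and the treated cut-off in standard units is a = c + 0.2231. The means of those who remain are:

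- control: −φ(c)/Φ(c)
- treated: −0.2231 − φ(a)/Φ(a)

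| | q = 5% | q = 10% |
|---|---|---|
| c; a | 1.645; 1.868 | 1.282; 1.505 |
| Treated share beyond cut, 1 − Φ(a) | 3.09% | 6.62% |
| Control mean | −0.1031/0.95 = −0.1086 | −0.1755/0.90 = −0.1950 |
| Treated mean | −0.2231 − 0.0697/0.9691 = −0.2951 | −0.2231 − 0.1286/0.9338 = −0.3609 |
| Difference | −0.1865 | −0.1659 |
| Estimated ratio | 0.830 | 0.847 |
| Log effect kept | 0.1865/0.2231 = 84% | 0.1659/0.2231 = 74% |
| Infants affected | 7.1 + 4.4 = 11.5 | 14.2 + 9.4 = 23.6 |

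At q = 2% the ratio is 0.816 and about 4 to 5 infants are affected. At q = 20% it is 0.872, with 62% of the log effect kept.

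**Step 3: the false early end.** Assume instead that these infants stay in but are recorded at 30% of the cut-off. Each arm's mean is then (truncated mean)·Φ + (c + ln 0.3)·(1 − Φ), with Φ taken at c for controls and at a for treated.

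- 5%: control −0.0811, treated −0.2723, difference −0.1912, ratio 0.826.
- 10%: control −0.1677, treated −0.3319, difference −0.1641, ratio 0.849.

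The attenuation is about the same as with exclusion.

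**Step 4: power and the null.** A simulation with 142 per arm, 3,000 runs and log-SD 1.0 used a true ratio of 0.75. With 10% of controls beyond the cut, power fell from about 0.68 to 0.53 under exclusion and to 0.59 under the early end. With a true ratio of 1.00, the expected estimate stayed at 1.00 and the type I error stayed at about 5% under either route.

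**The case against.** Several points on the other side stand.

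- **Home oxygen before the illness.** Because Protocol 6.1 admits infants with chronic lung disease, a reader might infer that infants on permanent home oxygen bias the comparison. They do not by themselves. Pre-illness oxygen is fixed before randomisation and is expected to balance under 1:1 allocation. The bias comes from post-treatment duration deciding who is lost.
- **Size.** A reader might infer that a real benefit could vanish. The figures do not support this: 74–84% of the log effect remains at 5–10%, and about 62% at 20%. Nor is there a false-positive risk in this model. A reader might also apply 5–10% to all 284 infants and count 14–28. Those rates are for controls, and the treated rates under the same model are lower.
- **Assumptions.** Every rate is assumed. A single cut-off is a simplification, since each infant is discharged at a different time.
- **Intent and visibility.** The restart sentence shows that a first stop was not meant to be the end, so the early-end fault is confined to a restart with no later stop. SAP 18 promises to quantify missing data with reasons where known, so exclusions should be visible, though not corrected.
- **Unseen sources.** The Post Mechanical Ventilation CRF guide is not supplied. If it records discharge as a stop, exclusion is avoided but a false early end replaces it. SAP 17.2 lists "Whether infant on oxygen supplementation upon arrival at PICU" for the baseline table, which does not show that nothing else on oxygen was collected. The protocol supplied is version 2.0, whereas the SAP cites versions 3.0 and 6.0.

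None of this supplies a rule for the infant still on oxygen at the last record.

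**Conclusion.** The concern holds in a limited form. Followed exactly, the SAP excludes infants still on oxygen at the end of data collection, or scores some of them at an earlier stop. Durations are understated, and a true benefit is pulled towards no difference. With no true effect, no bias between arms is expected.

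Under the stated assumptions (log-SD 1.0, true ratio 0.80, 5–10% of controls leaving on oxygen), exclusion moves the ratio from 0.80 to about 0.83–0.85 and affects about 12–24 of 284 infants. That infants will leave on oxygen is a reasonable inference, not a documented figure; if few do, the effect is small. One secondary outcome is concerned. The primary analysis and the sample size are unaffected.

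**What to change.** In SAP 17.4.5:

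1. Accept a stopped record as the end only if no later record shows oxygen.
2. Keep infants still on oxygen at their last record, and treat them as not having stopped. Either rank them longest in a rank-based comparison, or use a time-to-event analysis in which they stay at risk without the event up to a common horizon, with death on oxygen as a competing event. Simple censoring at discharge belongs only in a sensitivity analysis: infants who go home on oxygen are likely to need it longer, so that censoring is probably informative.
3. Report by arm the number leaving hospital on oxygen.

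A flag for pre-illness oxygen, taken from existing notes, is optional for description or a sensitivity analysis. The endpoint need not be redefined for those infants.

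The cost is SAP wording and a standard analysis on data already collected, with no extra patients or procedures. The downside is that the result is no longer a ratio of geometric means, so it will not be on the same scale as the primary outcome.
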